Project description:

Title:

Effects of metformin on hepatic fatty acid metabolism in patients with type 2 diabetes assessed by positron emission tomography.

Investigator and sponsor:

[name], consultant, PhD
Department of Nuclear Medicine & PET Center
[name]
[name]
[contact]
[contact]
[contact]

Version 2.4.1 - date 4/2 2013

Regional Scientific Committee Region Midtjylland: 1-10-72-522-12
Clinical Trials Gov ID: NCT01729156
Data Protection Agency: 1-16-02-303-12

Introduction and purpose:

Type 2 diabetes (T2D) is characterized by insulin resistance, impaired glycemic control and elevated levels of potentially harmful circulating lipids. One of the most widely used drugs to control blood sugar levels in patients with T2D is metformin, which has well known inhibitory effects on hepatic gluconeogenesis, but also possesses poorly understood lipid lowering effects. Thus, metformin suppresses circulating triglycerides to an extent that is not fully explained by decreased hepatic de novo lipogenesis. The pharmacological effects of metformin are thought to principally occur in the liver, which has been a serious obstacle to human studies. The liver is an inaccessible organ and any experimental procedures designed to uncover intracellular reactions has previously involved surgical procedures with biopsies. Advances in molecular imaging may change that. Positron emission tomography (PET) is a new and advanced technology in which tracer amounts of positron emitting isotopes are attached to the molecules under investigation, in this case fatty acids. This non-invasive technique allows quantification of the fate of fatty acids in the liver in vivo and can therefore be used to assess how large a proportion of lipids that are oxidized, reesterified or resecreted from the liver. It is therefore our aim to employ the PET scanning technique to study the effect of metformin on hepatic fatty acid handling in the liver in patients with type 2 diabetes.

Specific purposes:

- By [11C]palmitate PET scans to investigate hepatic fatty acid uptake, oxidation and resecretion as very-low-density-lipoprotein (VLDL) in a population of patients with newly diagnosed T2D. Patients will be studied in a parallel group, placebo controlled, double-blinded study before initiation of metformin therapy and after 3 months treatment. An age- and BMI matched group treated with metformin for 3 months will serve as healthy controls.
- By whole body [1-14C]VLDL-TG to quantitate hepatic production and secretion of VLDL-TG before and after metformin treatment.
- By 14CO₂-breath collection to quantitate the effect of metformin on whole body oxidation of VLDL derived fatty acids
- By [3-3H]glucose infusion to quantitate the impact of metformin on whole body glucose disposal as well as endogenous glucose production and to correlate any changes with changes in lipid metabolism
- By dual X-ray absorptiometry to determine the impact of metformin treatment on body composition

It is our hypothesis that T2D hypertriglyceridemia is primarily caused by defective hepatic oxidation of fatty acids with subsequent increased resecretion as VLDL-TG. We also hypothesize that treatment for 3 months with metformin will normalize hepatic fatty acid oxidation resulting in diminished reesterification and resecretion as triglycerides.

Background:

The prevalence of diabetes in general and T2D in particular has been growing steadily during the past decades(1). T2D is most often associated with obesity and is characterized by insulin resistance and elevated blood glucose but also by profound dyslipidemia. This is the so-called diabetic lipid triad of elevated low-density-lipoprotein (LDL) cholesterol, decreased high-density-lipoprotein (HDL) cholesterol and hypertriglyceridemia(2). Each component of the dyslipidemic triad is associated with

increased risk of cardiovascular disease and mortality and is therefore a potential risk factor for diabetic patients.

Triglycerides are transported in the circulation packaged in lipoproteins that are large particles consisting of scaffolding and surface proteins (among them ApoB's) with a core of various lipids. ApoB48 containing chylomicrons dominate in the immediate postprandial period, whereas ApoB100 containing VLDLs are secreted continuously albeit at a slower rate after feeding(3). VLDL associated TG (VLDL-TG) is formed in the liver by a series of processes involving reesterification of fatty acids released from subcutaneous and visceral adipose tissue depots. VLDLs serve as transport molecules ensuring a constant exchange of lipids between adipose tissue, muscle and the liver and also "absorb" any surplus fatty acids not oxidized by fuel consuming tissue and released due to bursts of exercise or catecholamine stimulation. In healthy humans, the total pool of circulating VLDLs is surprisingly stable as is the production, secretion and elimination of VLDL particles. In patients with diabetes, by contrast, release of fatty acids from adipose tissue depots exceeds what is oxidized in the liver and in muscle, and as a result, more fatty acids are reesterified and resecreted as VLDL-TG. This expands the VLDL-TG pool leading to diabetic hypertriglyceridemia. What causes this imbalance between released and oxidized fatty acids is still somewhat unclear. It has been argued that the major culprit is adipose tissue resistance with increased release of fatty acids, but also defects in insulin action in the liver and increased de novo lipogenesis due to elevated blood sugar has been suggested. To date, the precise pathophysiology remains obscure.

Treatment of diabetic hypertriglyceridemia is aimed at preventing formation of VLDL particles in the liver(4). Statins are a series of drugs originally designed to inhibit cholesterol production that also prevent hepatic formation of mature VLDL particles due to lack of cholesterol content. Inhibition of VLDL-TG substrate delivery to the liver can be achieved by blocking the hormone sensitive lipase with acipimox, a nicotinic acid analogue(5), or by increasing fatty acid oxidation with fibrates(6). Somewhat surprisingly, the glucose lowering biguanide, metformin, also reduces levels of circulating triglycerides. This has previously been attributed to diminished conversion of glucose to lipids via hepatic de novo lipogenesis, but recent studies indicate that metformin may affect lipid metabolism more directly(7), either in the liver or in the periphery. In vitro and animal studies have thus demonstrated that metformin may increase hepatocyte fatty acid oxidation(8). Metformin has also been shown to increase endothelial lipolysis of VLDL derived TGs(9) releasing more fatty acids for oxidation in muscle. Whether the effect of metformin is primarily hepatic or peripheral or a combination of both is still as unclear as whether diabetic dyslipidemia is caused by hepatic or peripheral insulin resistance. The advent of the PET technique may very well change this.

[figure not shown]
In short, the PET scan technique involves tracing the fate of certain metabolites in vivo. This is done by incorporating a positron emitting isotope into any molecule being investigated (the radiotracer), inject it as a bolus into the patient and subsequently monitor time-activity curves in various organs. Organ time-activity curves reflect radiotracer exchange between the circulation and intracellular pools e.g. lipid droplets in the liver or VLDL-TG particles ready for secretion. Using dynamic PET scans, Iozzo et. al have validated a kinetic model that accurately describe the hepatic fate of [C11]palmitate(10, 11) but [C11]palmitate can also be used to estimate myocardial fatty acid uptake and oxidation(12). PET scans are non-invasive and are in theory only limited by the field of view of the scanner, typically ~20 centimeter. Estimating fatty acid metabolism in a single scan is thus feasible in neighboring organs like the liver, visceral fat and myocardium (see figure 1).

In addition to the fatty acid tracer, we have in our lab developed and validated a whole body VLDL-TG tracer, [1-14C]VLDL, which enables measurements of VLDL-TG production, secretion and oxidation in tissues outside the PET scanner field of view(13, 14). Combining whole body [1-14C]VLDL tracer kinetics with [C11]palmitate PET scans thus yields simultaneous measurements of hepatic and peripheral lipid metabolism (see figure 2).

It is therefore our aim to establish whether the lipid lowering effect of metformin is a result of increased hepatic fatty acid oxidation or increased oxidation of VLDL derived TGs in skeletal muscle. Insights into the mechanisms of metformin action will provide us with an opportunity to tailor lipid lowering therapy in diabetes patients.

METHODS:

Design: The study will be a randomized, double-blinded, placebo-controlled parallel study with 24 newly diagnosed type 2 diabetes patients and 12 age, sex and BMI matched healthy controls. Patients and controls will be studied before intervention and after 3 months treatment with either metformin (2 x 1000 mg) or placebo (T2D patients). Healthy controls will be studied after 3 months metformin treatment (see figure 3).

Intervention T2D patients: Treatment with metformin or metformin placebo: 500 mg twice daily for 2 to 4 weeks followed by 1000 mg daily for the remaining 8-12 weeks. Dose will be reduced in patients with moderate renal insufficiency (eGFR 50-80 ml/min. = 25-50%, eGFR 30-50 ml/min. = 50-75%). Treatment will be initiated after day 0 for a total of 90 days. In this patient cohort, the study is double-blinded and randomized.

Intervention healthy controls: Treatment with metformin or metformin placebo: 500 mg twice daily for 2 to 4 weeks followed by 1000 mg daily for the remaining 8-12 weeks. Treatment will be initiated after day 0 for a total of 90 days. In this patient cohort, the study is not blinded –subjects serve as their own controls (before and after treatment).

Study subjects: 24 newly diagnosed T2D patients >50 years will be recruited by physicians in the endocrine outpatient unit (MEA, Aarhus University Hospital). 12 healthy controls will be recruited by advertisements in local papers.

Inclusion criteria patients:

- Newly diagnosed (>3 and <12 måneder) Type 2 diabetes
- Age 50-70 year
- BMI<40

Inclusion criteria healthy controls:

- Age 50-70 year
- Sex and BMI matched with included patients

Exclusion criteria patients

- Metformin treatment >6 months
- Liver disease in the form of NASH (non-alkoholic steatohepatitis)
- Cancer
- Anaemia
- HbA1C>8.5 %
- Other clinically relevant abnormal biochemical parameter
- Chronic or acute pancreatitis
- Known substance or alcohol abuse
- Allergy towards metformin
- Claustrophobia
- Extreme obesity > 130 kg

Study power: We have previously studied T2D patients and found that their average VLDL-TG secretion was ~87 $\mu\text{mol}/\text{min}$. Interventional studies using metformin to treat patients with type 2 diabetes report TG concentration decreases of ~10 % (15), 10 % (16), 13 % (17), 17 % (18) and 17 % (19) and an extensive meta-analysis of clinical studies have shown an average decrease of ~10 % (20). Total TG concentration reflects TG in all lipoprotein fractions but there are strong indications that metformin primarily affects VLDL associated TG. Since the proportion of TG in VLDL particles is 60-75 % (21), VLDL-TG concentration will decrease more than 10 %, estimated 14 %. In addition, we have previously observed a 50 % greater decrease in VLDL-TG *production* than VLDL-TG *concentration* during insulin stimulation (22). In our view, metformin treatment in the dose proposed by us will therefore result in a decrease in hepatic VLDL-TG production ~20 % or $0.20 \times 87 \mu\text{mol}/\text{min} = 17 \mu\text{mol}/\text{min}$. Based on our previous studies in comparable patient populations (23), the SD of VLDL-TG secretion

change is 13 $\mu\text{mol}/\text{min}$. α is set at 0.05 and power β set at 0.8. We will then have to recruit ~11 participants in each group.

Scans: *PET/CT scans:* PET/CT scans will be preceded by at least 6 hours fasting. A catheter will be placed in an antecubital vein for injection of the radiotracer. First, a low dose CT scan will be performed in order to aid anatomical localization of the liver and for attenuation correction of the subsequent PET scan. Second, 380 MBq [C11]palmitate is injected as a bolus over 10 seconds. Dynamic imaging of [C11]palmitate will be done by list mode acquisition of data in 32 frames of increasing length (from 5 s a frame in the first minute to 600 seconds a frame in the end of the PET study). The PET scan will last a total of 50 minutes. Arterialized blood samples will be obtained in order to measure radioactive palmitate metabolites (TGs, phospholipids and CO₂). The input function will be corrected for radioactive metabolites.

PET data analysis: *Kinetics:* Hepatic metabolism of the radiotracer [C11]palmitate will be calculated based on a 3-compartment model developed and validated by Iozzo et. al at Turku PET Center. In this model, the input function is based on image derived data from regions of interest (ROIs) in the aorta, portal vein and hepatic right lobe. The dual input from the hepatic artery and the portal vein will be weighted with 80 % to the portal vein and the remaining 20 % from the artery. The analysis yields the parameters hepatic fatty acid uptake (K₁), hepatic fatty acid oxidation (k₂), reesterification (k₃) and resecretion as VLDL-TG (k₄).

[1-14C]VLDL-TG metabolism: Study subjects will be transferred to the Medical Research Lab immediately after the PET scan and a bolus (~10 mCi) ex-vivo labeled [1-14C]VLDL will be injected. Blood samples will be taken every five minutes for 30 minutes and every 30 minutes for the following 2,5 hours in order to estimate VLDL-TG secretion. Oxidation of VLDL-TG will be assessed by collecting breath samples every 30 minutes and analyzing them for ¹⁴CO₂ content.

[3-3H]glucose metabolism: [3-3H]glucose will be infused continuously during the basal period and subsequently for another 2 hours during a hyper-insulinemic euglycemic clamp (HE clamp). HE-clamping is utilized to estimate whole body insulin sensitivity in subjects and can also be employed to assess hepatic endogenous glucose production.

Body composition: Both patients and healthy controls will have their body composition assessed by dual X-ray absorptiometry (DXA) (Hologic). In the DXA scanner, minute amounts of X-rays are used to determine various tissue attenuation patterns that reflect body composition.

Blood samples: Serum insulin, C-peptide, cortisol and glucagone will be measured by Radio-Immuno-Assay (RIA); interleukin-6 (Luminex); retinol binding protein 4 (Elisa); plasma

glucose (YSI STAT 2300 Glucose Analyzer), glycerol and lactate (Fluorometric enzymatic method), serum non-esterified FFAs (radiochemical assay), plasma acyl and desacyl ghrelin.

Patient data: Demographic data and other information regarding patients and disease history are collected before the onset of the trial. All information are recorded in the Case Report Form (CRF).

Data and permissions: All electronically collected data are archived on the PET Center server (Tiger). Manual data are kept in a locked room at the PET Center. All participants are registered under a study subject ID with initials provided by the blinding and randomization authority – The Hospital Pharmacy. Participants are aware that the local Ethical Committee and the Danish Data Agency must have access to all data. The study is approved by the Danish Medicines Agency (EUDRA-CT 2012-000808-16), The Danish Data Agency and the local Ethical Committee (1-16-02-303-12).

Radioactivity dose:

PET scan with low dose CT to determine hepatic fatty acid metabolism ($[^{11}\text{C}]$ palmitate):

According to the latest ICRP 106, maximal realistic effective dose for C11-labeled tracers is 0.011 mSv/MBq. We plan to inject 380 MBq per study day and the total injected dose will then be:

$$0.011 \text{ mSv/MBq} \times 380 \text{ MBq/day} \times 2 \text{ days} = 8,36 \text{ mSv.}$$

Low dose CT of the abdominal region is 1 mSv.

Total PET related radiation dose is then 9,36 mSv. The $[^{14}\text{C}]$ VLDL tracer yields an additional 0,4 mSv per study day and the DXA scan 0,15 mSv.

Accumulated radiation dose: 9,91 mSv.

This dose is roughly equivalent to half a diagnostic CT of the thorax, abdomen and pelvis (18 mSv). It is also equivalent to 3 times the normal background radiation (3 mSv per year).

For persons aged 60 this corresponds to an additional risk of dying from cancer of about 0.0005 (0.05 %) which is comparable to smoking 9 packets of cigarettes or driving 6000 kilometers in a car (<http://www.xrayrisk.com/> (24)).

Ethics:

The study is performed according to the principles of the Helsinki declaration II and has been approved by the local Ethical Committee, the Danish Medicines Agency and the Data

Protection Agency. All PET related procedures have been performed at the PET Center numerous times both in an experimental and a clinical setting. The Clinical Research laboratory has extensive experience in doing metabolic studies and has experienced no serious adverse study related events for the past 5 years.

Rationale for the study:

Hypertriglyceridemia is almost universally present in patients with T2D and has been convincingly demonstrated to be a serious risk factor for the development of cardiovascular disease (CVD). Since CVD is associated with an increased morbidity and mortality, many ongoing studies are designed to foster ideas of how to lower potentially dangerous circulating lipids. In this context, it is of great interest to determine whether the lipid lowering effect of metformin is independent of its beneficial effects on glucose metabolism and whether the effect indeed hinges on improved or "normalized" hepatic fatty acid oxidation. If that is the case, future lipid lowering treatment strategies in patients with T2D should include drugs with a different mode of action, e.g. statins or liraglutide rather than fibrates. This study is therefore directly designed to modify treatment of a large group of patients and the risk of using ionizing radiation (category 2B) is in our opinion acceptable. To further minimize radiation related risks, the study is restricted to patients >50 years.

Publication:

[name], [name] and other associated researchers will cooperate in gathering data, interpreting results and writing the papers. All results, both negative and positive, will be reported. The Vancouver Criteria will be adhered to.

Reference list

2. Goldberg IJ. Diabetic Dyslipidemia: Causes and Consequences. *Journal of Clinical Endocrinology & Metabolism* 2001;86(3):965-71. doi: 10.1210/jc.86.3.965.
3. Beisiegel U. Lipoprotein metabolism. *European heart journal* 1998;19 Suppl A:A20-3.
4. Haffner SM. Management of dyslipidemia in adults with diabetes. *Diabetes care* 1998;21(1):160-78.

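### The protocol gives two metformin maintenance doses, 2000 mg/day under Design and 1000 mg/day under both Intervention paragraphs

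*Protocol*

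**What the plan says.** The metformin dose appears in three places in the Methods section of the protocol.

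- **Design** has participants studied "after 3 months treatment with either metformin (2 x 1000 mg) or placebo (T2D patients").
- **Intervention T2D patients** has "500 mg twice daily for 2 to 4 weeks followed by 1000 mg daily for the remaining 8-12 weeks".
- **Intervention healthy controls** repeats the same schedule: "Intervention healthy controls: Treatment with metformin or metformin placebo: 500 mg twice daily for 2 to 4 weeks followed by 1000 mg daily".

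Both Intervention paragraphs fix the length of treatment: "Treatment will be initiated after day 0 for a total of 90 days". The patient paragraph adds a renal rule in percentages with no base dose in mg: "Dose will be reduced in patients with moderate renal insufficiency (eGFR 50-80 ml/min. = 25-50%, eGFR 30-50 ml/min. = 50-75" per cent). No other visible text states a metformin dose. The Study power paragraph ties the assumed fall of about 20 % in VLDL-TG production to the dose the investigators propose, but gives no figure for that dose. Figure 3, which Design cites, is not shown in the text available.

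**The concern.** The objection is to the contradiction, not to either dose. The Intervention paragraphs set out a two-phase schedule, yet both phases add up to the same daily amount. Only the number of intakes per day could change. A lead-in followed by a maintenance phase normally means the dose goes up, and the dose it would go up to is the one in Design. As written, the detailed dosing instructions and the design statement differ by a factor of two.

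The dose is the intervention under test. The Intervention paragraphs cover all 36 planned participants: 24 patients on metformin or matching placebo, and 12 controls. Someone preparing medication from those paragraphs would supply half of what Design describes for the whole maintenance phase. A reader of the results could not tell from the protocol which exposure was planned. The renal reductions carry the same doubt, because they are percentages of a dose that is not settled.

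**Working it through.** **Inputs (all from the protocol Methods).** Design: 2 x 1000 mg, taken as a daily amount; the word daily is not written there, but this is the natural reading. Intervention: 2 x 500 mg per day for 2 to 4 weeks, then 1000 mg per day. Duration: 90 days.

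**Daily dose**

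- Design: 2 x 1000 = 2000 mg/day.
- Intervention, first phase: 2 x 500 = 1000 mg/day.
- Intervention, second phase: 1000 mg/day.
- Increase between phases as written: 1000 - 1000 = 0 mg/day.
- Ratio of maintenance doses: 2000 / 1000 = 2.

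**Days at maintenance**

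- After a 2-week lead-in: 90 - 14 = 76 days.
- After a 4-week lead-in: 90 - 28 = 62 days.

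**Cumulative dose per participant on metformin**

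| | 2-week lead-in | 4-week lead-in |
|---|---|---|
| Intervention text as written | 90 x 1 g = 90 g | 90 x 1 g = 90 g |
| Design dose after the lead-in | 14 x 1 + 76 x 2 = 166 g | 28 x 1 + 62 x 2 = 152 g |
| Mean daily dose, Design reading | 166 / 90 = 1.844 g | 152 / 90 = 1.689 g |
| Shortfall of the Intervention text | 166 - 90 = 76 g | 152 - 90 = 62 g |
| Share delivered | 90 / 166 = 54 % | 90 / 152 = 59 % |

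**Renal reductions.** Assumption: the stated percentages are amounts taken off the dose.

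| eGFR (ml/min) | Reduction | Base 2000 mg/day | Base 1000 mg/day | Gap (mg/day) |
|---|---|---|---|---|
| 50-80 | 25-50 % | 1000-1500 | 500-750 | 500-750 |
| 30-50 | 50-75 % | 500-1000 | 250-500 | 250-500 |

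The ratio is 2 in each row. This is the same discrepancy carried forward, not a second defect.

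**Does it reach the sample size?** The Study power paragraph uses a difference of 17 µmol/min, SD 13, alpha 0.05 (taken as two-sided) and power 0.80. By the normal formula, n = 2 x (1.96 + 0.84)² x 13² / 17² = 9.2, rounded up to 10 per group. The t-test solution is 10.2, rounded up to 11, which matches the protocol's figure of about 11. No mg amount enters the formula, so the sample size does not change.

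**The case against.** The strongest reply is that this is an evident drafting slip. Inserting one word, to give 1000 mg twice daily, turns the lead-in into a real increase and makes all three statements agree. No other edit as small does both. Staff who read the whole Methods section would meet both statements, and nothing in the protocol ranks the Intervention paragraphs above Design. The sample size stands, the blinded comparison stands, and no one is shown to have been given the wrong dose. On that view it is a wording correction of modest weight.

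Much of this is right. The dropped word is the most likely explanation, and the cumulative figures only restate one factor of two. The count of 36 also needs qualifying: it is the number the text covers, not the number exposed. If the patients are allocated 1:1, which is an assumption, 12 patients and 12 controls, so 24 people, would take metformin. The number of participants in the renal strata cannot be known from the protocol.

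The reply does not remove the contradiction. The wording occurs twice, in the two paragraphs that describe the treatment, and a reader counting statements would find two for 1000 mg/day and one for 2000. A missing figure might state a dose, but it could agree with only one of the two versions. That a careful reader can guess the intended dose does not make the written dose correct.

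**Conclusion.** The concern holds, and the text must be fixed. Maintenance is 2000 mg/day under Design and 1000 mg/day under Intervention, and the written titration raises the daily total by nothing. Followed literally, the Intervention paragraphs give 54 to 59 % of the cumulative dose that the Design reading implies over 90 days, a shortfall of 62 to 76 g per participant on metformin.

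This rests on reading 2 x 1000 mg as a daily amount and on the Design dose being reached straight after a 2- or 4-week lead-in. The renal figures further assume that the percentages are reductions. The sample size and the validity of the randomised comparison are not affected. The seriousness comes only from the twofold difference in the written dose of the study drug. The protocol does not settle which dose was intended.

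**What to change.** The sponsor should decide the maintenance dose and state it once, consistently.

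- **If Design is right:** change both Intervention paragraphs to *500 mg twice daily for the first 2 to 4 weeks, then 1000 mg twice daily to the end of the 90 days*.
- **If Intervention is right:** change Design to 1000 mg daily and remove the step, which then serves no purpose.
- **In either case:** add a clause saying that the renal percentages are reductions of that dose, if that is what is meant. Check the Hospital Pharmacy's dispensing instructions against the corrected text. Those instructions are not shown; Data and permissions names the pharmacy only as the authority for blinding and randomisation.

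The cost is a wording change in two paragraphs (or in Design plus removal of the step), one added clause and one check. The sample size and the analysis stay as they are.

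### The accumulated radiation dose of 9.91 mSv counts the 14C-VLDL tracer for one study day instead of two; the protocol's own components sum to at least 10.31 mSv

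*Protocol*

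**What the plan says.** The Radioactivity dose section of the protocol builds the total from four items.

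- **11C-palmitate:** 0.011 mSv/MBq × 380 MBq per day × 2 days = 8.36 mSv.
- **CT:** "Low dose CT of the abdominal region is 1 mSv", which brings the PET-related subtotal to 9.36 mSv.
- **14C-VLDL and DXA:** the 14C-labelled "VLDL tracer yields an additional 0,4 mSv per study day and the DXA scan 0,15 mSv".
- **Result:** "Accumulated radiation dose: 9,91 mSv".

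The same section then likens this dose to about half of an 18 mSv diagnostic CT, to 3 times a yearly background of 3 mSv, and to an added risk of cancer death of about 0.0005 at age 60. Under Rationale for the study, the protocol names a risk category (2B) and judges the radiation risk acceptable.

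The visit schedule appears elsewhere. Specific purposes uses the VLDL tracer "to quantitate hepatic production and secretion of VLDL-TG before and after metformin treatment". Design states "Patients and controls will be studied before intervention and after 3 months treatment".

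**The concern.** The 11C line is multiplied by two study days. The 14C line, although expressed per study day, is not. A total described as accumulated should treat both alike if both tracers are given on both days, so the published sum looks too low.

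What is at stake is the accuracy of a safety statement and not the trial's inference. The comparisons with diagnostic CT, background and cancer mortality all start from this number, as does the argument that the exposure is acceptable. Those exposed include 12 healthy controls as well as 24 patients. The error also runs in the favourable direction.

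**Working it through.** **1. Reproduce the stated figure.**

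- 11C: 0.011 × 380 × 2 = 8.36 mSv
- plus CT: 8.36 + 1 = 9.36 mSv, matching the stated subtotal
- plus 14C once and DXA once: 9.36 + 0.4 + 0.15 = 9.91 mSv, matching the stated total

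Among the combinations of one or two CTs, one or two 14C doses and one or two DXA scans, only the one that counts each of the three once gives 9.91.

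**2. Is the 14C tracer given on two days?** Four places in the protocol say so.

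- Specific purposes plans VLDL-TG kinetics before and after metformin.
- Design studies patients and controls at both times.
- The [1-14C]VLDL-TG metabolism paragraph injects the bolus right after the PET scan, so it falls on the same days that the 11C line multiplies by two.
- Study power rests on the SD of the change in VLDL-TG secretion (13 µmol/min), and a change needs two measurements.

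**3. Correct the certain item.** With 14C = 2 × 0.4 = 0.8 mSv:

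8.36 + 1 + 0.8 + 0.15 = 10.31 mSv, and 10.31 / 9.91 = 1.040.

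**4. Items that can only raise the sum or leave it unchanged.**

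- *CT.* Scans places a CT before the PET scan: "First, a low dose CT scan will be performed in order to aid anatomical localization of the liver". The dose section pairs the two as well: "PET scan with low dose CT to determine hepatic fatty acid metabolism". Two PET days therefore mean two CTs. Whether 1 mSv is the dose of one CT or of both is not stated. Per scan seems the likelier reading, but it is not certain.
- *DXA.* The number of scans is not given. Specific purposes uses DXA to assess the impact of treatment, which suggests two. Whether 0.15 mSv is per scan is not stated either.
- *[3-3H]glucose.* It is infused in the basal period and during the clamp, but has no line in the sum. No activity or dose is given, so it cannot be sized here.

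**5. Range and effect on the comparisons** (tritium excluded). The risk column scales the protocol's 0.0005 in proportion to dose, for example 0.0005 × 10.31 / 9.91 = 0.00052. That proportionality is an assumption.

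| Reading | Sum (mSv) | Ratio to 9.91 | Fraction of 18 mSv CT | Years of 3 mSv background | Scaled risk |
|---|---|---|---|---|---|
| As stated | 9.91 | 1.000 | 0.55 | 3.30 | 0.00050 |
| 14C ×2 | 10.31 | 1.040 | 0.57 | 3.44 | 0.00052 |
| 14C ×2, DXA ×2 | 10.46 | 1.056 | 0.58 | 3.49 | 0.00053 |
| 14C ×2, CT ×2 | 11.31 | 1.141 | 0.63 | 3.77 | 0.00057 |
| 14C ×2, CT ×2, DXA ×2 | 11.46 | 1.156 | 0.64 | 3.82 | 0.00058 |

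**The case against.** The strongest reply is that the error is immaterial. The certain part is 0.40 mSv. At 10.31 mSv the fraction of a diagnostic CT goes from 0.55 to 0.57 and the background multiple from 3.3 to 3.4, and the protocol offers these comparisons only as approximations. The 11C term makes up 8.36 / 10.31 = 81 % of the corrected sum and uses a coefficient described as the realistic maximum, so none of these figures is a measured dose. This stands, and it limits how much weight the point deserves. It does not excuse a total that disagrees with its own parts.

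The CT reading is also open to challenge. The author marks 11C and 14C as per study day but not the CT, and the CT line follows a two-day figure and feeds a two-day subtotal. One mSv for both scans is therefore possible. The background multiple approaches 4 only if 1 mSv is per scan, so that consequence is conditional.

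The risk comparison is too coarse to carry much. A source figure of about 0.0005, given to one digit, could be anything from 0.00045 to 0.00055. Scaled, that is 0.00047 to 0.00057 at 10.31 mSv and 0.00051 to 0.00063 at 11.31 mSv. Either total could round to 0.0005 or 0.0006.

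Finally, one sentence in Design places the healthy controls only after 3 months of metformin. It conflicts with the preceding sentence and with Intervention healthy controls, which says "subjects serve as their own controls (before and after treatment". Two visits is the better reading, and nothing in that sentence touches the 24 patients.

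**Conclusion.** The concern holds. The stated 9.91 mSv omits one of two planned 14C-VLDL doses, and the protocol's own components give at least 10.31 mSv per participant studied on both days, 4 % more. This needs no outside figure; it rests only on the per-day label and the two-visit schedule.

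The upper readings, up to 11.46 mSv (+16 %), depend on CT and DXA doses being per scan and on DXA being done twice. Tritium would come on top by an unknown amount. At the certain minimum the protocol's comparisons remain nearly intact. If CT is per scan, 3 times background becomes nearly 4 times. The protocol does not define the limits of the risk category it names, so no consequence for that category can be shown from the document. This should be fixed as a matter of accurate safety information; sample size, design and analysis are untouched.

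**What to change.** Restate the total with each source counted for every visit on which it is given:

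- 11C ×2 (8.36 mSv) and 14C ×2 (0.8 mSv);
- CT ×2, unless 1 mSv already covers both scans, with the figure labelled as per scan or total;
- DXA by the number of scans done, labelled in the same way;
- a line for [3-3H]glucose, with its activity and dose.

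Then update the comparisons with diagnostic CT, background and cancer risk, and confirm that the stated risk category still applies. Carry the corrected total into any other document that repeats it.

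The cost is a few lines and a slightly less favourable stated dose.
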